Aim 3: Test acceptability, feasibility, and preliminary effectiveness of EBIS to target implementation mechanisms and outcomes relative to implementation as usual (IAU) via a pilot randomized clinical trial with 40 community clinicians. Our primary Aim 3 dependent variables are EBIS acceptability and feasibility, measured through questionnaires, interviews, and recruitment and retention statistics. Secondary outcomes are preliminary effectiveness of EBIS on implementation outcomes (SSAI adoption and fidelity), and engagement of target implementation mechanisms (clinician anxiety and self-efficacy related to SSAI use), assessed via mixed methods (questionnaires, chart-stimulated recall, observer-coded role plays, and interviews). We also will gather data on other possible implementation mechanisms (e.g., SSAI knowledge, attitudes, intentions, norms, and organizational factors). Qualitative interviews with clinicians will probe for contextual implementation barriers to SSAI use not addressed by EBIS to inform augmentation prior to fully powered evaluation.

1. Study Instruments:

Aim 1: N/A

Aim 2: Data will consist of responses to semi-structured interviews and completion of a brief survey about clinician background and perceptions related to work with patients at risk for suicide. Qualitative data will be integrated to iteratively adapt and refine the EBIS implementation strategy in preparation for the Aim 3 trial. All data will be used exclusively for research purposes.

- The qualitative interview guide and Aim 2 brief survey battery was previously reviewed and approved by the IRB

Aim 3: Clinical trial data will consist of clinician responses to self-report questionnaires, chart-stimulated recall, semi-structured interviews, and fidelity role-plays with research staff. In addition, recruitment and retention

statistics will capture feasibility metrics. *No identifiable data about patient level information will be collected.* All data will be used exclusively for research purposes and will be administered at the following time points: T1 = baseline/pretraining; T2 = post-training; T3 = 2-week follow-up; T4 = 12-week follow-up. Specific measures that will be administered are described below. Table 2 shows the anticipated assessment battery for the Aim 3 clinical trial. All measures will be administered to all clinicians enrolled in the trial, regardless of assigned condition.

Primary Outcomes: Acceptability & Feasibility

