 - This measure was previously reviewed and approved by the IRB.
- **Clinician Demographics.** Brief questionnaire about clinician demographic (e.g., age, sex) and professional characteristics (e.g., years of experience, theoretical orientation, caseload descriptions), work setting, and a question about the clinician's person experience with suicide (e.g., "Have you ever had a client die by suicide while under your care?"). This will be administered at Time 1.
 - This measure was previously reviewed and approved by the IRB.
- **Anxiety Sensitivity Index (ASI-3).** Questionnaire about the clinician's physical, cognitive, or social concerns about anxiety. This will be administered at Time 1.
 - This measure was previously reviewed and approved by the IRB.
- **Organizational Innovation Specific Capacity for Suicide Prevention Evidence-based practices (OISCSE).** Questionnaire about the organizational policies, procedures, and practices within the clinician's organization to observe potential factors that could influence use of SSAI's. This measure has 14-items on a Likert scale plus a yes or no question to query any additional factors about the clinician's organization not mentioned in the first 14-items. If the clinician responds positively, they are asked an additional open response question. This measure was adapted from a previously developed measure to assess policies and procedures needed to support exposure therapy delivery, guided by responses to qualitative interviews completed in Aim 2 of this study and items from the Zero Suicide Organizational Self-Study in collaboration with suicide prevention and implementation science experts.
 - A copy of this measure is included for the IRB's review.

Table 2. Assessment Schedule for Aim 3

Outcome	Measure	T1	T2	T3	T4
Primary Outcomes					
EBIS Acceptability	Acceptability of Intervention Measure; Qualitative Interview (T4 only)		X		X
EBIS Feasibility	Feasibility of Intervention Measure; Recruitment/Retention statistics		X		X
Secondary Outcomes					
Target Implementation Mechanisms					
Clinician Anxiety	Subjective Units of Distress Scale; ⁷¹ Suicidal Patient Comfort Survey ⁵⁵ ; Anxiety Sensitivity Index (ASI-3) (Time 1 only)	X	X	X	X
Clinician Self-efficacy	Established question stems ⁸¹	X	X	X	X
Implementation Outcomes					
SSAI use (CSSRS, SPI)	Chart Stimulated Recall ⁸²	X		X	X
SPI Fidelity	Role Play coded w/ SPIRS			X	X
Additional Implementation Mechanisms of Interest					

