SSAI Knowledge	Self-Perceived Knowledge About Suicide Scale ⁸³	X	X		X
SSAI Attitudes	Attitudes Toward Suicide Prevention; ⁸⁴ Clinician Attitudes Toward Safety	X	X	X	X

	Planning ⁸⁵				
SSAI Intentions	Established question stems ⁸¹		X	X	X X
SSAI Norms	Established question stems ⁸¹		X	X	X X
Demographics	Demographics survey		X		
Organizational Factors	Organizational Innovation Specific Capacity for Suicide Prevention Evidence-based practices (OISCSE)		X		
T1=baseline. T2=post-training. T3=2-week. T4=12-week follow-up.					

2. Group Modifications:

Aims 1 and 2: N/A

Aim 3: After consenting to participate, clinicians will be randomly assigned to one of the two implementation conditions; the measurement battery will be identical for clinicians in each condition, with the exception that qualitative interviews for clinicians randomized to the EBIS condition will include several additional questions about their specific experience with EBIS.

3. Method for Assigning Subjects to Groups:

Aim 1: N/A

Aim 2: No participants will be randomized as a part of Aim 2 activities.

Aim 3: Clinician participants will be randomized 1:1 to receive either Implementation as Usual (IAU) or IAU+EBIS. Randomization will take place after the informed consent process and prior to beginning either training condition.

4. Administration of Surveys and/or Process:

Aim 1: N/A

Aim 2: To accomplish Aim 2, we will deliver the draft version of EBIS as outlined in the procedures below. Following receipt of the draft version of EBIS, clinicians will complete brief 45-60 minute qualitative interviews with trained study staff. Qualitative interviews will take place via phone, videoconference, or in person, depending on participant preference.

Aim 3: During the clinical trial, all measures will be administered by trained research staff in accordance with the assessment schedule outlined above. Questionnaires at each time point will be administered either in paper format or electronically using REDCap, depending on participant preference (See *Study Instruments* above). Qualitative interviews will take place via phone, videoconference, or in person, depending on participant preference.

5. Data Management:

Drs. [name] (PI) and [name] (co-PI) will oversee all data cleaning and management with support from co-Investigator [name].

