In this prototyping phase, EBIS will be administered either individually to clinicians or in small groups of 2-4 clinicians. The syllabus that will guide EBIS administration is included for the IRB's review. All trainings and consultation sessions will be video recorded and transcribed using HIPAA compliant software. During administration, study staff will take field notes on implementation challenges. Clinicians will complete a brief demographic questionnaire before and after completing the training. After receiving EBIS, clinicians will complete brief qualitative interviews (45-60 minutes) about their experience with EBIS either virtually or at a private location (e.g., the University of Pennsylvania campus or your office location). Interviews will be audio-recorded and transcribed. The first part of the interview will query clinicians on acceptability and feasibility of EBIS. The second part will comprise semi-structured questions about perceptions of how EBIS influenced anxiety and self-efficacy to deliver the CSSRS and SPI. The last part will solicit suggestions for improvements to optimize EBIS. Clinicians will also receive continuing education credits for training activities. We anticipate it will take clinicians approximately 4-5 hours to complete study procedures (up to 4 hours of training and 1 hour for the interview).

We will make iterative refinements after each EBIS administration in response to observed implementation challenges and clinician feedback until saturation is reached (anticipated maximum: 20 clinicians). When clarity is needed on whether certain adaptations are needed, we will return to our Advisory Board for guidance.

The finalized manual that will guide EBIS administration in Aim 3 was submitted for the IRB's review.

Aim 3: Test acceptability, feasibility, and preliminary effectiveness of EBIS to target implementation mechanisms and outcomes relative to implementation as usual (IAU) via a pilot randomized trial.

After consenting, clinicians will be randomized to one of two implementation arms: IAU (n=20), or EBIS (n=20), which comprises all IAU activities plus EBIS as refined in Aim 2. If a clinician drops out of the study prior to attending their initial workshop (which is when official randomization will occur), we will make efforts to replace that individual to obtain a final sample of 40 clinicians randomized.

IAU Condition. Gold-standard IAU for SSAs typically comprises pre-implementation

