Quantitative analyses This pilot feasibility trial is not intended to be adequately powered to detect significant effects.^{94,95} Findings will provide key preliminary data to support the feasibility of EBIS and study procedures for a fully powered R01 (e.g., frequency of suicidal ideation over the 8-week follow-up period). Qualitative analysis of interview transcripts and mixed methods analysis will supplement quantitative analyses.

Preliminary Analysis. Data screening and missing data analysis will be conducted in accordance with best practice recommendations.⁹⁶ Prior to conducting main analyses, we will examine the psychometric properties of all scales used to assess constructs of interest (e.g., coefficient alpha) to confirm adequate performance. We will conduct analyses of baseline variables as a randomization check to ensure comparable baseline characteristics for clinicians in EBIS and IAU. Any differences will be controlled for in subsequent analyses.

Hypothesis 1: EBIS will be an acceptable and feasible implementation strategy. We will calculate descriptive statistics on the AIM and FIM measures and compare scores between EBIS and IAU. We will also evaluate EBIS feasibility by calculating the proportion of clinicians randomized to EBIS who complete all exposure tasks.

Exploratory Hypotheses 1 and 2: EBIS will engage target implementation mechanisms of clinician anxiety and self-efficacy better than IAU; clinicians randomized to EBIS will show improved SSAI adoption and fidelity relative to clinicians randomized to IAU. We will examine the effect of condition over time on target mechanisms (anxiety and self-efficacy) and implementation outcomes (mean CSSRS screening frequency across encounters, proportions of appropriate encounters in which clinicians conduct follow-up assessment with the CSSRS and SPI use, as measured by CSR, and average SPI fidelity scores on role plays) using repeated measures analysis of covariance (ANCOVA), controlling for organization (given the small sample size and that we will recruit from only a small number of organizations for this pilot, we do not anticipate the need for multilevel analysis).

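### Choosing covariates by chance baseline imbalance leaves the between-arm models undetermined; name them in advance instead

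*Combined protocol and SAP*

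**What the plan says.** Under STUDY PROCEDURES, section 5 (Statistical Analysis), the Preliminary Analysis paragraph states: "We will conduct analyses of baseline variables as a randomization check to ensure comparable baseline characteristics for clinicians in EBIS and IAU". The next sentence is the rule at issue: "Any differences will be controlled for in subsequent analyses". The plan does not say what counts as a difference, which variables are candidates, whether a variable must be related to the outcome, or how many may enter.

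The preliminary step precedes the main analyses, and Hypothesis 1 follows it directly. That hypothesis covers the primary outcomes ("Our primary Aim 3 dependent variables are EBIS acceptability and feasibility") and calls for descriptive statistics and a comparison of AIM and FIM scores between arms, with no model named. The only named model is the repeated measures ANCOVA for the exploratory hypotheses, with organization as a covariate.

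The pool of baseline variables is wide. METHODS, section 1 describes the demographics form as: "Brief questionnaire about clinician demographic (e.g., age, sex) and professional characteristics (e.g., years of experience, theoretical orientation, caseload descriptions), work setting". It adds an item on the clinician's own experience with suicide. Table 2 schedules a further set of scales and the chart-stimulated recall (CSR) at T1. AIM and FIM are collected only at T2 and T4, and the SPI role play only at T3 and T4, so none of these three has a T1 value.

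**The concern.** Allocation is random: "Clinician participants will be randomized 1:1 to receive either Implementation as Usual (IAU) or IAU+EBIS". Provided T1 is unaffected by knowledge of the assigned arm, any baseline difference is chance. Whether a variable differs by chance says nothing about whether it predicts the outcome. Selecting on imbalance has three consequences:

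- The covariate set, and so the fitted model, cannot be written down before the baseline data by arm have been examined.
- A variable chosen because it tracks arm is the most expensive kind to adjust for, unless it also explains outcome variance.
- A strongly prognostic variable that happens to balance is omitted, and the precision it would have given is lost.

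At stake are the reproducibility and precision of the estimates meant to inform the later, fully powered study.

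**Working it through.** **Inputs from the protocol.** The target is "to obtain a final sample of 40 clinicians randomized", split equally, so 20 per arm. There are 3–5 organizations. No power calculation, significance level or imbalance threshold is given, so there is no planned figure to reproduce.

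**Candidate count (mine; the plan has no list).** Seven personal or professional items (age, sex, experience, orientation, caseload, work setting, experience with suicide), plus ASI-3 and OISCSE, make 9. Adding 8 T1 survey scales (SUDS, patient comfort, self-efficacy, knowledge, two attitude scales, intentions, norms) and 3 CSR measures gives 20. Counting CSR once gives 18.

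**Assumptions not in the protocol.** A difference means two-sided p<0.05; candidates are independent and normal; the model is linear for one outcome at one time point, without an organization term.

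**Step 1, one borderline covariate.** t(0.975, 38) = 2.024, a standardized difference of 2.024 × √(2/20) = 0.64. The share of arm explained is 2.024²/(2.024² + 38) = 0.097. The variance of the arm effect is multiplied by 1/(1 − 0.097) = 1.108. Interval width is multiplied by √1.108, about 1.05, with a negligible change from losing one degree of freedom. At p = 0.01 the same arithmetic gives about 1.09.

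**Step 2, how often the rule triggers and what it costs if candidates are non-prognostic.** The chance of at least one flag is 1 − 0.95^k and the expected number is 0.05k. Width changes are simulated test-then-adjust models relative to the unadjusted interval; simulated trigger rates were 36–65%.

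| Candidates k | At least one flagged | Expected flagged | Mean width | Mean width when triggered |
|---|---|---|---|---|
| 9 | 37% | 0.45 | +4% | +10% |
| 12 | 46% | 0.60 | +5% | +10% |
| 18 | 60% | 0.90 | +7% | +12% |
| 20 | 64% | 1.00 | +8% | +12% |

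With a common correlation of 0.3 among 12 candidates, the trigger rate falls to 40% and the mean widening is about 4%.

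**Step 3, if the flagged covariate is prognostic.** With a single flagged covariate, mean width is +3% at a correlation of 0.3 with the outcome, −5% at 0.5 and −20% at 0.7. Break-even is about 0.35. For a covariate exactly at p = 0.05 it is √(1 − 1/1.108) = 0.31; averaged over all flagged covariates it is slightly under 0.4.

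**Step 4, selecting versus naming in advance.** With one prognostic variable (correlation 0.5 to 0.7) among 18 candidates, the imbalance rule still gives intervals 5–6% wider on average, because that variable is usually not the one flagged. Always adjusting for it gives intervals 12% narrower at 0.5 and 27% narrower at 0.7.

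**Step 5, Type I error.** Under test-then-adjust it is about 0.05 with non-prognostic covariates and about 0.036–0.043 with a prognostic one at correlation 0.5–0.7. It is not inflated.

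**The case against.** The strongest reply is that many candidates are probably prognostic. BACKGROUND presents self-efficacy as an independent predictor of SSAI use, OISCSE is collected because organizational factors may affect use, and several T1 scales are the exploratory outcomes' own baselines. This stands: treating every candidate as non-prognostic is close to a worst case for the exploratory contrasts. It is more plausible for AIM and FIM, which have no baseline value. It does not rescue the rule, which never asks whether a variable is prognostic and drops those that balance (Step 4).

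A second reply is that no AIM/FIM model or interval is specified, so there is nothing to widen. It is true that none is named. But the adjustment sentence has no exemption, and controlling for a variable in a comparison of scores requires some adjusted analysis, so the gap is real.

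A third is that the plan says: "This pilot feasibility trial is not intended to be adequately powered to detect significant effects". That lowers the consequence, since no decision threshold rests on interval width. It does not make an undetermined model useful as preliminary evidence.

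**Conclusion.** The point holds as a defect of specification with a modest cost in precision. The rule selects on chance imbalance, leaves the between-arm models open until baseline data are seen, and omits prognostic variables that balance. The 4–8% average widening, and 10–12% when triggered, rest on an assumed p<0.05 rule, 9–20 independent non-prognostic candidates and 20 per arm.

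A reader might infer more than the documents support:

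- **That the added covariates would be non-prognostic.** This is an assumption, and the protocol itself suggests otherwise for some T1 measures.
- **That intervals would be nearly 30% wider.** This needs a cut-off such as a standardized difference above 0.25, together with 20 non-prognostic candidates. Each variable then has a 43% chance of entering and the simulated mean widening is 29%. No such cut-off is in the protocol; a looser rule would cost more than p<0.05, but the plan does not say which applies.
- **That few degrees of freedom would remain.** With intercept, arm, 2–4 terms for organization and one flagged covariate, 40 clinicians leave 33–35.
- **That the estimand changes.** None is stated, and main-effect adjustment in a linear model under randomization targets the same mean difference.
- **That every later analysis is affected.** The EBIS-only proportion completing exposure tasks and the qualitative work cannot be adjusted for arm imbalance. Only between-arm comparisons are in scope.

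**What to change.** Delete the sentence "Any differences will be controlled for in subsequent analyses". Replace the randomization check with a table of baseline characteristics by arm, descriptive and without tests. Then state the covariates for each between-arm comparison:

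- **Outcomes with a T1 value** (anxiety, self-efficacy, CSR measures): organization plus the outcome's own T1 value.
- **Outcomes without one** (AIM, FIM, SPI fidelity): organization plus at most one or two T1 variables, chosen for expected prognostic value and named before any data by arm are seen. The investigators should choose these; T1 self-efficacy is an obvious candidate for fidelity.
- **Observed imbalance**: adjust for it only in a labelled sensitivity analysis.

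The AIM/FIM paragraph should also say which model is used for the comparison. The change takes a few sentences in the analysis section and needs no new data. The downside is that a chance imbalance in a prognostic variable not on the list shows up only in the sensitivity analysis.

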- **Acceptability of Intervention Measure:** A 4-item, psychometrically-validated measure that indexes the extent to which stakeholders believe an implementation strategy (in this case, IAU or EBIS) is acceptable. This will be administered at Time 2 and Time 4.
 - o This measure was previously reviewed and approved by the IRB.
- **Feasibility of Intervention Measure.** A 4-item, psychometrically-validated measure that indexes the extent to which stakeholders perceive an implementation strategy (in this case, IAU or EBIS) is feasible. This will be administered at Time 2 and Time 4.
 - o This measure was previously reviewed and approved by the IRB.
- **Qualitative Interview.** This interview will consist of three sections. Section 1 will query about the acceptability of the implementation condition to which they were assigned (EBIS or IAU) and any barriers that arose in engaging with any component of the study. Section 2 will focus on how the implementation condition engaged target implementation mechanisms. The final section will be guided by the Consolidated Framework for Implementation Research to query about barriers to SSAI use, with the primary goal of identifying contextual determinants of use not adequately addressed by EBIS. This will be administered at Time 4.
 - o This measure was previously reviewed and approved by the IRB.

Secondary Outcomes: Target Implementation Mechanisms

- **Subjective Units of Distress Scale (SUDS).** The SUDS is a one-item, 10-point rating scale of perceived distress, commonly used to guide exposure therapy. This will be administered at Time 1- 4.
 - o This measure was previously reviewed and approved by the IRB
- **Suicidal Patient Comfort Survey.** A brief, 5-item measure assessing clinician anxiety about interacting with and treating patients with suicidality. This will be administered at Time 1- 4.
 - o This measure was previously reviewed and approved by the IRB.
- **Self-Efficacy Questionnaire.** Established question stems from behavioral measuring clinicians' perceptions of themselves as having the skills and abilities to perform a task (in this case, SSAI use) on a 7-point scale. This will be administered at Time 1- 4.
 - o This measure was previously reviewed and approved by the IRB.

Secondary Outcomes: Implementation Outcomes

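### Does leaving recruitment and retention rates undefined keep clinicians lost before the workshop out of the feasibility evidence?

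*Combined protocol and SAP*

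**What the plan says.** The Aim 3 overview under Methods states: "Our primary Aim 3 dependent variables are EBIS acceptability and feasibility, measured through questionnaires, interviews, and recruitment and retention statistics". Table 2 lists, in the primary feasibility row, "Feasibility of Intervention Measure; Recruitment/Retention statistics". Study Instruments adds that these statistics serve as feasibility metrics.

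Hypothesis 1 in the Statistical Analysis section sets out two quantitative steps. The first is "We will calculate descriptive statistics on the AIM and FIM measures and compare scores between EBIS and IAU". The second is "We will also evaluate EBIS feasibility by calculating the proportion of clinicians randomized to EBIS who complete all exposure tasks". It gives no formula, denominator or time point for recruitment or retention. Of the AIM and the FIM alike, Study Instruments says: "This will be administered at Time 2 and Time 4". T2 falls directly after training.

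On allocation, Method for Assigning Subjects to Groups says: "Randomization will take place after the informed consent process and prior to beginning either training condition". The Detailed Description for Aim 3 deals with a clinician who "drops out of the study prior to attending their initial workshop (which is when official randomization will occur". In that case "we will make efforts to replace that individual to obtain a final sample of 40 clinicians randomized".

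Subject Follow-up commits the team to recording who enrolls, why others do not, and who leaves, with weekly monitoring of enrollment and retention.

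**The concern.** A measure listed as primary has no written calculation. The two calculations that are written begin at or after the workshop: exposure completion counts clinicians already randomized, and the questionnaires are first given after training. Someone who consents, drops out before the workshop and is replaced appears in neither figure.

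That loss is informative in a pilot. Participation takes about 17 hours over 12 weeks, and a larger trial needs to know how many clinicians to consent. With no denominator fixed, retention could be reported from consent or from randomization once the data are known, and the second can only look equal or better. The adjective *official* before randomization might also hint at an earlier working assignment. If so, replacement would remove clinicians who already had an arm.

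**Working it through.** **No plan figure to reproduce.** The documents state no expected loss, retention target, power or effect size. The only arithmetic is 20 + 20 = 40 randomized, which agrees with the stated sample.

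**Inputs.** Forty randomized, 1:1 (Detailed Description, Aim 3). Assumed, because the documents are silent: k consented clinicians lost before the workshop and replaced, and 36 of the 40 randomized reaching T4.

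**Formulas.** Workshop attendance among the consented = 40/(40 + k). T4 retention from consent = 36/(40 + k). Intervals are exact (Clopper-Pearson) 95%. They are approximate here, since recruitment continues until 40 are randomized.

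| k | Attendance, 40/(40 + k) | T4 retention from randomization | T4 retention from consent |
|---|---|---|---|
| 0 | 40/40 = 100% (91.2–100) | 36/40 = 90.0% (76.3–97.2) | 36/40 = 90.0% (76.3–97.2) |
| 2 | 40/42 = 95.2% (83.8–99.4) | 90.0% | 36/42 = 85.7% (71.5–94.6) |
| 4 | 40/44 = 90.9% (78.3–97.5) | 90.0% | 36/44 = 81.8% (67.3–91.8) |
| 8 | 40/48 = 83.3% (69.8–92.5) | 90.0% | 36/48 = 75.0% (60.4–86.4) |

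The denominator can therefore matter numerically. But the last column is the product of the two before it: 36/(40 + k) = (36/40) × 40/(40 + k). For k = 4, 0.900 × 0.909 = 0.818. The numbers consented, randomized and completing T4 yield every version, so a participant flow showing all three settles the ambiguity.

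**Do those losses affect the written calculations?** No. Someone lost before the draw has no arm and has received no EBIS. Eighteen completers among 20 randomized to EBIS would be 90% (68.3–98.8) whatever k is, and that is the correct reading of exposure completion. It cannot be carried over to all consented clinicians, because half of those randomized receive IAU and are never offered exposure. Literally, 18/42, 18/44 and 18/48 are 42.9%, 40.9% and 37.5%, and none of these measures the feasibility of EBIS.

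**Would a later trial be mis-sized?** Only if its planner applied a from-randomization rate to a count of consents. Then 100/0.90 = 111.1 consents would give 111.1 × 0.857 = 95.2, 111.1 × 0.818 = 90.9 or 111.1 × 0.750 = 83.3 completers. Nothing in the documents proposes that step.

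**Is there an earlier assignment?** Set side by side, one section puts randomization after consent and before training, and the other puts it at the initial workshop. The second is a more precise form of the first. No section describes a provisional allocation.

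**The case for a change.** The strongest case for a change is that a primary measure should be defined before its data are seen, that feasibility is a main product of a pilot not powered for effects, and that the wording would cost a few sentences. Subject Follow-up gives improvement of recruitment procedures as the use of its tracking data and defines no outcome statistic. The enrollment benchmarks do not say whether they count consented or randomized clinicians. The interviews take place at T4 and so miss early losses too.

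These textual points are correct, and defining the rates would be tidier. They do not show that the evidence is missing. Recruitment statistics ordinarily cover the period before randomization, the plan names them as feasibility metrics, and the counts are collected. No retention threshold or go/no-go rule depends on the denominator, so choosing one cannot turn a failed criterion into a pass.

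One possible addition, consented over eligible and approached, is generally not observable. Under Subject Recruitment and Screening, agencies pass the materials to their own staff and the team contacts only clinicians who express interest. The remark about *official* randomization rests on one adjective and does not stand.

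**Conclusion.** No change follows. The Statistical Analysis section leaves numerators and denominators unwritten for descriptive rates that the plan names elsewhere and whose data it collects. Analysts would fill this with a standard participant flow from consent through randomization to T2, T3 and T4, with replaced clinicians still counted among the consented.

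The effect on the between-arm comparison and on exposure completion is nil. The effect on a quoted T4 retention figure is zero with no replacements and, with 36 of 40 reaching T4, 4, 8 or 15 percentage points with 2, 4 or 8 replaced. The flow counts make any such gap visible.

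This rests on two assumptions: the workshop draw is the only allocation, as both sections on randomization indicate, and the tracked enrollment and dropout counts are reported. The loss counts are illustrative; the documents supply none.
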